#### **4.5.3. Exploratory Safety Variables**

Exploratory safety endpoints include:

- Change in high sensitivity C-reactive protein (hsCRP) from baseline to week 12
- Change in alkaline phosphatase from baseline to week 12

#### **4.5.4. Adverse Events of Special Interest**

No AESIs have been defined for this study.

#### **4.5.5. Acute Intravenous Infusion Reactions**

Infusion reactions are defined as any relevant AE that occurs during the infusion or within 2 hours after the infusion is completed. All infusion reactions must be reported as AEs and graded using the grading scales as instructed in the protocol.

#### **4.5.6. Laboratory Safety Variables**

The clinical laboratory tests include blood chemistry, hematology, urinalysis, urine chemistries, hs-CRP, and others. Samples for laboratory testing are to be collected at the time points specified in the Schedule of Events ([Table 3](#)). Clinical laboratory values are in standard international (SI) units, including associated normal ranges provided by the central laboratory, and grouped by function in summary tables. Clinical laboratory values in conventional (US) units are also to be available in the database, with associated normal ranges. For laboratory measurements performed at local laboratories, the corresponding local laboratory normal ranges will be used.

Both actual test values and “change from baseline” values (defined as the post-baseline value minus the baseline value) are used in central lab result summaries. Potentially clinically significant values (PCSV) ranges are to be applied to central lab test values as applicable (see [Appendix 11.2](#) for PCSV definitions).

#### **4.5.7. Vital Signs**

The following vital signs parameters are to be collected according to the Schedule of Events in [Table 3](#):

- Body temperature (°C)
- Semi-recumbent/2-minute standing systolic and diastolic blood pressures (mmHg) and heart rate (bpm)
- Respiratory rate (bpm)

Both actual values and “change from baseline” values (defined as the post-baseline value minus the baseline value) are to be used in the result summaries. Potentially clinically significant values (PCSV) ranges are to be applied to the vital sign parameter values as applicable (see Appendix 11.2 for PCSV definitions).

#### 4.5.8. Orthostatic Hypotension

A patient is to be determined to have orthostatic hypotension if any of the following criteria are met:

- If the semi-recumbent systolic blood pressure is  $<160$  mm Hg, a decrease in the 2-minute standing systolic blood pressure of  $\geq20$  mm Hg or a decrease in the standing diastolic blood pressure of  $\geq10$  mm Hg from the semi-recumbent systolic or diastolic blood pressure, respectively

OR

- If the semi-recumbent systolic blood pressure is  $\geq160$  mm Hg, a decrease in the 2-minute standing systolic blood pressure of  $\geq30$  mm Hg or a decrease in the standing diastolic blood pressure of  $\geq15$  mm Hg from the semi-recumbent systolic or diastolic blood pressure, respectively

OR

- An increase in the 2-minute standing heart rate of  $\geq30$  bpm from the semi-recumbent heart rate.

OR

- The patient is unable to stand for standing blood pressure measurements due to dizziness or lightheadedness

In case any of the following criteria are met, up to 2 re-checks (within approximately 5 minutes of the original measurement) should be performed (patient should remain standing). An AE of orthostatic vital sign change should be reported if the change is confirmed upon the repeat tests.

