- Use of a monoamine reuptake or monoamine oxidase inhibitor is acceptable if used for treatment of anxiety and/or depression at a stable dose during at least 3 months prior to screening
- If in the judgement of an investigator a monoamine reuptake or a monoamine oxidase inhibitor is used for treatment of both pain and anxiety/depression at a stable dose during at least 3 months prior to screening, use of the monoamine reuptake or monoamine oxidase inhibitor is acceptable if the investigator is able to provide appropriate documentation (eg, medical records with appropriate diagnoses, clinical opinions of the patient's treating physicians, documentation of the investigator's clinical opinion).

10. History or presence at the screening visit of multiple sclerosis, autonomic neuropathy, diabetic neuropathy, or other peripheral neuropathy

11. Significant concomitant illness including, but not limited to, psychiatric, cardiac, renal, hepatic, neurological, endocrinological, metabolic, or lymphatic disease that, in the opinion of the investigator, would adversely affect the patient's participation in the study
12. History of hospital admission for depression or suicide attempt within 5 years or active, severe major depression at screening
13. Resting heart rate of <45 beats per minute (bpm) (by vital sign assessment or as captured during electrocardiogram [ECG] assessment) or history or presence of second- or third-degree heart block at the screening visit. Resting heart rate may be rechecked up to 2 times at the screening visit.
14. History or presence of orthostatic hypotension at the screening visit. If the initial assessment for orthostatic hypotension is positive, orthostatic vital signs can be repeated up to 2 more times to confirm orthostatic hypotension prior to making the decision to exclude the patient. Refer to Section 8.2.3.2 for more information regarding this assessment.
15. History of poorly controlled hypertension, as defined by:
  - Systolic blood pressure  $\geq 180$  mm Hg or diastolic blood pressure  $\geq 110$  mm Hg at the screening visit
  - Systolic blood pressure of 160 mm Hg to 179 mm Hg or diastolic blood pressure of 100 mm Hg to 109 mm Hg at the screening visit, AND a history of end organ damage (including history of left ventricular hypertrophy, heart failure, angina, myocardial infarction, stroke, transient ischemic attack, peripheral arterial disease, and moderate-to-advanced retinopathy [hemorrhages or exudates, papilledema]).

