### 8.2.3.2. Orthostatic Vital Sign Assessment

Orthostatic blood pressure and heart rate are measured with the patient lying semi-recumbent for 10 minutes and after standing for 2 minutes. Prior to starting an assessment of orthostatic blood pressure and heart rate, patients should ambulate for at least 5 minutes. This assessment will be performed at the specified visits ([Table 1](#)).

In case any of the following criteria are met, up to 2 re-checks (within approximately 5 minutes of the original measurement) should be performed (patient should remain standing):

If the semi-recumbent systolic blood pressure is <160 mm Hg, a decrease in the 2-minute standing systolic blood pressure of  $\geq 20$  mm Hg or a decrease in the standing diastolic blood pressure of  $\geq 10$  mm Hg from the semi-recumbent systolic or diastolic blood pressure, respectively

OR

If the semi-recumbent systolic blood pressure is  $\geq 160$  mm Hg, a decrease in the 2-minute standing systolic blood pressure of  $\geq 30$  mm Hg or a decrease in the standing diastolic blood pressure of  $\geq 15$  mm Hg from the semi-recumbent systolic or diastolic blood pressure, respectively

OR

An increase in the 2-minute standing heart rate of  $\geq 30$  bpm from the semi-recumbent heart rate.

An AE of orthostatic vital sign change should be reported if the change is confirmed upon the repeat tests.

If the patient is unable to stand for standing blood pressure measurements due to dizziness or lightheadedness, the patient is considered to have orthostatic hypotension, which should be reported.

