#### **5.8.3. Analysis of Vital Signs**

Vital signs - temperature, blood pressure, heart rate (semi-recumbent and standing), orthostatic blood pressure/heart rate, and respiration rate- are to be summarized by baseline and change from baseline to each scheduled assessment time with descriptive statistics by treatment group and combined REGN5069 for the SAF, for treatment period and follow-up period.

PCSV summary including orthostatic hypotension is to be constructed for treatment period, period and overall during the study, as well as presented in a listing.

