## 6.4. Visit Windows

By-visit analysis (including efficacy, laboratory data, vital signs, ECG, ADA) is summarized by the nominal visit number. Assessments taken outside of protocol allowable windows are displayed according to the case report form (CRF) assessment recorded by the investigator. For assessments without a nominal visit number such as Unscheduled, EOT, and EOS assessments, a visit number is assigned based on the actual visit date using the study day analysis window based on the targeted visit study day in [Table 3](#) Schedule of Events.

The following visit windows are to be used to map the unscheduled visits, early end of treatment visits, early study termination visits and daily electronic dairy entries, based on the study day:

Visit No.	Visit	Targeted Study Days*	Analysis Window in Study Days
1	Screening	Day -30 to Day -1	$\geq -30$ and $\leq -1$
2	Baseline**	1	1
3	Week 1	8	[2, 11]
4	Week 2	15	[12, 22]
5	Week 4	29	[23, 43]
6	Week 8	57	[44,71]
7	Week 12	85	[72,99]
8	Week 16	113	[100,127]
9	Week 20	141	[128,155]
10	Week 24	169	[156,183]
11	Week 28	197	[184,211]
12	Week 32	225	[212,239]
13	Week 36	253	[240,309]
14	Week 52	365	$\geq 310$

\*Study days are calculated from the first dose of study drug (Day 1).

\*\*For the purpose of change-from-baseline calculations, if a patient has missing data on Day 1 (Baseline Visit), the closest available data from the screening visit window may be used, unless otherwise specified.

If multiple measurements occur within the same visit window, the following rules are to be used to determine the analysis value:

- When multiple valid measurements occur within the same visit window, the one closest to the target study day is used in the analysis.
- When multiple valid measurements occur within equal distance from the target study day, the value after the target study day is used in the analysis.

Both scheduled and unscheduled measurements are considered for determining abnormal/PCSV values from laboratory, vital sign or ECG as well as the baseline values.

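### SAP 4.5.8 turns the protocol's re-check triggers into a single-reading definition of orthostatic hypotension, not linked to confirmation and in conflict with Table 5

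*SAP*

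**What the plan says.** SAP 4.5.8 introduces its list with: "A patient is to be determined to have orthostatic hypotension if any of the following criteria are met". The criteria are:

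- a systolic fall of at least 20 or a diastolic fall of at least 10 mm Hg when semi-recumbent systolic pressure is below 160;
- falls of at least 30 or 15 mm Hg when it is 160 or more;
- a standing heart-rate rise of at least 30 bpm;
- inability to stand because of dizziness or lightheadedness.

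The re-checks and the adverse-event rule come only after the list.

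Protocol 8.2.3.2 gives the same pressure and heart-rate cut-offs a different role: "In case any of the following criteria are met, up to 2 re-checks (within approximately 5 minutes of the original measurement) should be performed". It continues: "An AE of orthostatic vital sign change should be reported if the change is confirmed upon the repeat tests". It applies the term orthostatic hypotension outright, with no repeat, only to the patient who cannot stand. Exclusion criterion 14 refers to that section and says "orthostatic vital signs can be repeated up to 2 more times to confirm orthostatic hypotension prior to making the decision to exclude the patient".

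For reporting, SAP 5.8.3 says "PCSV summary including orthostatic hypotension is to be constructed for treatment period", with a listing. SAP 4.5.7 and 5.8 place PCSV definitions in Appendix 11.2. The orthostatic row of Table 5 there uses the same pressure falls but joins them with *and* to a heart-rate rise of at least 30 bpm. It has no re-check and no baseline condition. SAP 6.4 adds: "Both scheduled and unscheduled measurements are considered for determining abnormal/PCSV values from laboratory, vital sign or ECG".

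**The concern.** A list that tells the site when to measure again has become the list that makes a patient a case. Read literally, a fall that disappears on the re-check a few minutes later still counts as orthostatic hypotension in the derived variable. So does an isolated heart-rate rise, which the protocol, once confirmed, calls only an orthostatic vital sign change. The derived count and the adverse-event count can then disagree about the same reading.

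This matters because protocol 3.2.1 names sympathetic blockade, with possible effects on blood pressure, among the serious potential risks and lists orthostatic monitoring as a safeguard. Protocol Table 1 schedules the test at eight post-baseline visits (weeks 1, 2, 4, 8, 12, 16, 24 and 36), so false positives have eight chances to accumulate per patient.

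**Working it through.** **Where confirmation applies.** In the protocol, crossing a cut-off leads to a re-check, and a confirmed change leads to an adverse event. At screening, a positive result may be repeated before exclusion. In SAP 4.5.8, crossing a cut-off leads directly to the classification, and confirmation governs only the adverse event. SAP 5.8.3, SAP 6.4 and Table 5 contain no rule by which a normal re-check cancels a positive.

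**Document figures.** The documents give no orthostatic rate and no reading error. They supply 80 patients per group and eight visits. The plan's own power statement concerns WOMAC pain and supplies only the group size here. It reproduces: 80 × 0.85 = 68 evaluable per group, difference 1.1 and SD 2.3 give 79.6%, against the stated 80% or so.

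**Assumptions (none from the documents).** There is no drug effect.

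- Mean standing-minus-semi-recumbent change in systolic/diastolic/heart rate: −2/+2/+8.
- Between-patient SD: 4/3/4.
- Within-patient SD of the difference: three settings, shown in the table.
- Semi-recumbent systolic pressure is taken as below 160.
- The initial reading and the re-check share the semi-recumbent reading, because the patient stays standing; standing errors are independent.
- Patients confirmed positive at screening or baseline are removed.

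A single-reading case is ΔSBP ≤ −20 or ΔDBP ≤ −10 or ΔHR ≥ 30 at one or more visits. There were 200,000 simulated patients per setting.

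| Within-patient SD | One reading (4.5.8), 5 / 8 visits | First re-check confirms, 5 / 8 visits | Table 5 *and*, 8 visits |
|---|---|---|---|
| 5/3.5/5 | 3% / 5% | 0.7% / 1% | 0.0% |
| 7/5/5 | 14% / 20% | 3.6% / 5.5% | 0.01% |
| 10/6/7 | 33% / 46% | 11% / 17% | 0.2% |

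Per group of 80 over eight visits:

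- One reading: 80 × 0.05 = 4 to 80 × 0.46 = 37 false cases.
- First re-check confirms: 80 × 0.01 = 0.8 to 80 × 0.17 = 13.6.
- Table 5 as printed: at most 80 × 0.002 = 0.16.

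**Cross-check with other assumptions.** SD of one reading 5/3/4, 6/4/5 and 8/5/6; mean changes −2/+2/+6, −4/+1/+8 and −5/0/+8; systolic–diastolic error correlation 0.5; no between-patient variation; visits independent. The single-reading rate per visit is p = 0.76%, 5.07% and 14.97%. Then 1 − (1 − p)^8 gives 5.9%, 34.0% and 72.7%. With one confirming repeat the eight-visit figures are 0.6%, 8.8% and 35.8%; under the Table 5 rule they are 0.5% or less. The direction is the same and the range is wider. The heart-rate criterion adds little to the count (per visit, 4.99% rises to 5.07% in the middle setting and 14.56% to 14.97% in the noisiest). Its problem is mainly the label.

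**Dilution.** Take a true excess of 10 points with n = 80 per group and power ≈ Φ(d/√[(p₁q₁ + p₂q₂)/n] − 1.96).

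- From a 3% background: 3% against 13%, Φ(0.10/0.0422 − 1.96) = 0.66 (about 0.65 with a pooled variance).
- From a 15% noise background, the excess shows only in the 85% not already counted: 10 × 0.85 = 8.5 points. So 15% against 23.5%, Φ(0.085/0.0620 − 1.96) = 0.28.

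No test is planned on this table; the figures only show how far noise can blur a contrast.

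**The case against.** The strongest reply is that SAP 5.8.3 reports orthostatic hypotension as a PCSV, and PCSVs are defined in Table 5. If Table 5 governs as printed, noise produces almost no cases. A reader might infer from 4.5.8 that reading error alone will fill the safety table; the documents do not establish that. Nor do they rule it out. Appendix 11.2 describes its criteria as a reference, to be settled by the study team, while 4.5.8 is the section written to define this variable. The conflict stands, and the large figures apply only if 4.5.8 governs.

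A reader might also infer that the SAP abandons confirmation. It does not: 4.5.8 keeps the re-checks and repeats the protocol's adverse-event rule. Confirmed on-treatment changes therefore reach the TEAE tables, and 5.8.3 also summarises orthostatic pressure and heart rate as change from baseline. The derived variable is not the only place where a blood-pressure effect could appear.

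Three further points carry weight:

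- No Table 5 row requires a repeat, so a sensitive single-reading flag beside confirmed adverse events is a defensible convention, provided it is labelled as such.
- Confirmation loses true cases. With a true mean systolic fall of 22 and SD 7, detection per visit drops from about 61% to 45%.
- The protocol is not strict either. Exclusion 14 permits repeats rather than requiring them, 8.2.3.2 does not say whether one or both re-checks must confirm, and footnote 5 to Table 1 points to 8.2.3.2 for the definition of orthostatic hypotension as well as for re-checking.

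**Conclusion.** The point holds as a defect of definition. SAP 4.5.8 makes one unconfirmed reading a case and calls an isolated heart-rate rise hypotension. No SAP section links the derived variable to the re-check, and Table 5 gives a different rule.

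The size depends on which rule drives the summary and on assumed reading error. With no drug effect, the eight-visit rate is about 5% to 46% under 4.5.8, about 1% to 17% if the first re-check must confirm, and 0.2% or less under Table 5 (up to 0.5% in the cross-check). Confirmation reduces noise cases but does not remove them, partly because the re-checks share the semi-recumbent reading.

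A reader might infer a bias towards one arm. The documents do not support that: the noise falls on all arms alike, so it inflates incidence and dilutes contrasts in a descriptive safety table. The primary analysis is untouched. This should be corrected, but it does not threaten the trial's main conclusion.

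**What to change.** Reconcile SAP 4.5.8, 5.8.3 and Table 5 with protocol 8.2.3.2 so that one stated definition drives the PCSV summary, and say whether one or both re-checks must confirm. The choice of clinical criterion is the sponsor's. Then report as separate, labelled rows:

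- (a) findings confirmed on the protocol's re-check, or inability to stand;
- (b) initial readings that met a cut-off without confirmation;
- (c) isolated heart-rate rise, not labelled hypotension.

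SAP 1.2.4.2 shows that version 2.0 was written after the unblinded week-12 results were reviewed. The rows should therefore be added beside the existing definition, not substituted for it, so that no safety definition is replaced after the fact.

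The cost is SAP wording and two or three table rows; the protocol already calls for the re-checks. The small downside is that a case with no re-check done appears only in row (b).

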#### 4.5.9. 12-Lead Electrocardiography (ECG)

A standard 12-lead ECG is to be performed according to the Schedule of Events in Table 3 with the patient in the semi-recumbent position for approximately 10 minutes and prior to blood samples being drawn. Heart rate is recorded from the ventricular rate and the PR/PQ, QRS, and QT, QTcF intervals, and ECG status (normal, abnormal not clinical significant or abnormal clinical significant) is also recorded.

QTcF is defined as follows:

$$\text{QTcF (ms)} = \text{QT/RR}^{1/3},$$

where QT is the uncorrected QT interval measured in ms, and RR is 60/HR with HR being the heart rate in beats per minute.

Potentially clinically significant values (PCSV) ranges are to be applied to the ECG parameter values as applicable (see Appendix 11.2 for PCSV definitions).

#### **4.5.10. Physical Examination (PE) Variables**

No PE variables are defined, as, if clinically significant PE abnormalities are observed, an AE is entered. Otherwise no PE examination information is collected.

#### **4.5.11. Neurological Examination Variables**

A full or brief neurological examination is to be performed at the time points indicated in [Table 3](#). Neurological evaluations of specific domains as listed in the protocol are to be described as normal or abnormal not clinically significant or abnormal clinically significant.

Neurological findings at baseline that are not exclusionary should be recorded in the medical history. Findings at subsequent visits are to be assessed by the investigator to determine if these should be recorded as an AE. Clinically significant neurological abnormalities are recorded and will be summarized.

#### **4.5.12. Other Safety Variables**

- Joint Pain Questionnaire: A joint pain questionnaire is to be completed by the patient at the time points indicated in the Schedule of Events in [Table 3](#). For each knee, hip, and shoulder joint, the patient is prompted to indicate if he or she has experienced worse pain. Assessments include:
  - Patients with significantly worse joint pain in any joint at each scheduled visit
  - Patients with significantly worse joint pain by joint at each scheduled visit
- Joint replacement: an end-of-study phone call was to be conducted at approximately 52 weeks after the first dose of study drug. The purpose of the end-of-study phone call was to determine whether a patient underwent, is scheduled for, or is on a waiting list to receive joint replacement surgery, or whether joint replacement was recommended but the patient elected to defer since his/her last in-clinic visit. Patients were to also be asked to submit pre-operative imaging (X-ray and MRI, if available) for adjudication and to provide joint material for histological and molecular analyzes, if feasible. Assessments included:
  - Patients with joint replacement (all joint replacements)
  - Reason for joint replacement (all joint replacements)
  - Time to joint replacement (all joint replacements)
- Knee society score for joint replacement: an investigator-completed questionnaire that is used to objectively measure a patient's ability to function before and after total knee arthroplasty

As the study will now end when the last patient completes the week 36 visit, the week 52 phone call will not be performed for most of the patients; all available Joint Replacement information will be summarized in a listing.

## 4.6. Imaging

Radiographs of patients' knees, hips, and shoulders are to be taken using a standard approach at the time points indicated in Appendix 11.1, [Table 3](#). In addition to scheduled imaging, radiographs should be considered for worsening joint pain. The investigator is to consult the sponsor prior to scheduling additional imaging. Magnetic resonance imaging of the index knee is to be performed at the time points indicated in Appendix 11.1, [Table 3](#). In addition to scheduled MRIs, an MRI should be considered for worsening joint pain and if X-rays are inconclusive. The investigator is to consult the sponsor prior to scheduling additional imaging. If a patient undergoes a joint replacement surgery, patients will have additional radiographs at the time points indicated in [Table 4](#).

As described in the Charter for Arthropathy Adjudication Committee, the screening and on-study radiographs of the knees and hips are to be evaluated for joint space width to identify excessive loss of joint space. In addition, all radiographs and MRI scans are to be evaluated for the presence of adjudicated arthropathy. See Appendix 11.1, [Table 3](#), Arthropathy Adjudication, for details on adjudication criteria.

The imaging data summaries and listings will include:

- Adjudicated accelerated arthropathy (AA):
  - Patients and events of AA
  - Subtypes of AA
  - Patients and events of destructive arthropathy (DA)
  - Time to AA
  - Time to DA
- Clinically Significant Imaging Events not Considered Arthropathies
- Adjudicated Arthropathy Findings at Event-Driven Imaging Timepoint
- Adjudicated Arthropathy Imaging Events at EOT (Week 12) or EOF (Week 36) Imaging Timepoint
- Joint replacements:
  - Patients with joint replacement
  - Time to joint replacement

